### **5.3 Agent Ordering**

The drug will be delivered by Genentech to the Stanford Investigational Drug Services (IDS).

Per Stanford standard operating procedures, the Stanford IDS will be responsible for storage of atezolizumab and dispensing of the drug after subjects are screened and enrolled to the study.

### **5.4 Agent Accountability**

The Sponsor Investigator of the study will ensure maintenance of complete and accurate records of the receipt, dispensation, and disposal or return of all study drug in accordance with 21 Code of Federal Regulations (CFR), Part 312.57 and 312.62 and Genentech requirements.

All unused remaining product at the end of the study should be disposed of at the study site according to institutional standard operating procedure. If there is no SOP at the site for drug destruction, return study drug with the Inventory of Returned Clinical Material form as directed by Genentech.

## **6. DOSE MODIFICATIONS**

No dose modification for atezolizumab is allowed.

## **7. ADVERSE EVENTS AND REPORTING PROCEDURES**

The safety plan for patients in this study is based on clinical experience with atezolizumab in completed and ongoing studies. The anticipated important safety risks are outlined below (see Section 7.1).

Measures will be taken to ensure the safety of patients participating in this study, including the use of stringent inclusion and exclusion criteria and close monitoring of patients during the study. Administration of atezolizumab will be performed in a monitored setting in which there is immediate access to trained personnel and adequate equipment and medicine to manage potentially serious reactions. Guidelines for managing patients who experience anticipated adverse events, including criteria for treatment discontinuation, are provided in Appendix I. Refer to Sections 7.2-7.6 for details on safety reporting (e.g., adverse events, pregnancies) during the study.

### **7.1 Potential Adverse Events**

Atezolizumab has been associated with risks such as the following: IRRs and immune-related hepatitis, pneumonitis, colitis, pancreatitis, diabetes mellitus, hypothyroidism, hyperthyroidism, adrenal insufficiency, hypophysitis, Guillain-Barré syndrome, myasthenic syndrome or myasthenia gravis, meningoencephalitis, myocarditis, nephritis, and myositis. Immune-mediated reactions may involve any organ system and may lead

to hemophagocytic lymphohistiocytosis and macrophage activation syndrome. Refer to Appendix 9 of the protocol and Section 6 of the Atezolizumab Investigator's Brochure for a detailed description of anticipated safety risks for atezolizumab.

## 7.2 Safety Parameters and Definitions

Safety assessments will consist of monitoring and reporting adverse events and serious adverse events per protocol. This includes all events of death and any study-specific issue of concern.

The Stanford Cancer Institute Data and Safety Monitoring Committee (DSMC) will be the monitoring entity for this study. The DSMC will audit study-related activities to determine whether the study has been conducted in accordance with the protocol, local standard operating procedures, FDA regulations, and Good Clinical Practice (GCP). This may include review of the following types of documents participating in the study: regulatory binders, case report forms, eligibility checklists, and source documents. In addition, the DSMC will regularly review serious adverse events and protocol deviations associated with the research to ensure the protection of human subjects. Results of the DSMC audit will be communicated to the IRB and the appropriate regulatory authorities at the time of continuing review, or in an expedited fashion, as needed.

In addition to the DSMC above, no more than six patients at a time will be permitted to be dosed concurrently. More specifically, we will limit the accrual rate to this such that a maximum of 6 patients at any one time will be in the window between immunotherapy dosing and 10 days post recovery from definitive surgery. All patient safety data for this study will be reviewed by Drs. [name] and/or [name], and documented on the AE log. If there are any adverse events (Grade 3 or higher or serious of any grade) attributed to checkpoint inhibitor treatment, further enrollment to the study will be put on hold until the attribution is understood and the protocol has been modified accordingly (with IRB notification and approval) to mitigate the future risks to patients. Our statistical design was powered with the least number of patients necessary to achieve our primary objective. If during the course of the study, the number of patients who fail to complete the neoadjuvant protocol (due to drug related toxicity or tumor progression) is such that the primary objective would be unachievable, the study will be stopped early. Based on our statistical design, if at any point during the study, 4 patients fail to complete the neoadjuvant protocol, the study will be stopped early.

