## **3. PARTICIPANT SELECTION AND ENROLLMENT PROCEDURES**

### **Refer to the Participant Eligibility Checklist in Appendix A.**

Patients with advanced surgically-resectable cutaneous squamous cell carcinoma will be screened for enrollment in this study to yield 20 evaluable patients

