#### **10.1 Primary and Secondary Outcome measures**

The primary outcome measure for each patient is an indicator for successfully completing 3 cycles of neoadjuvant atezolizumab, followed by surgical resection of remaining disease. The treatment will be evaluated as non-feasible for patients who have disease progression during neoadjuvant treatment, discontinue study medications due to toxicity, or are not able to undergo curative surgical resection after the 3 cycles of treatment.

Patients who decline surgical intervention after completing the neoadjuvant treatment will be considered as having successfully received neoadjuvant treatment.

In this study, feasibility was chosen as the primary endpoint to assess whether patients can successfully complete the neoadjuvant treatment without significant disease progression precluding curative surgical resection, and with acceptable toxicity. Since the patient population will include tumors that are resectable at presentation (and patients will be medically fit to undergo surgery), any postponement of definitive surgical resection will need to demonstrate that this does not adversely affect the opportunity for curative therapy. If this postponement of surgery proves to not cause harm and administration of neoadjuvant treatment is feasible, this study may add an additional cohort to evaluate a combination of immune checkpoint inhibitors in this setting. Future studies can be designed that evaluate additional clinical endpoints.

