### **12. STATISTICAL CONSIDERATIONS**

#### **12.1 Statistical Design**

The primary objective is to determine the feasibility of three doses of atezolizumab prior to surgery in patients with advanced cutaneous squamous cell carcinoma. Our baseline assumption is that 50% of the population will complete all 3 doses of atezolizumab and then proceed to surgery. We can prove that with 20 patients by showing that 85% of the patients enrolled will complete the 3 neoadjuvant cycles of PD-L1 and then proceed to surgery. We will also be collecting demographic and descriptive data on tumor characteristics, and therapies. Please refer to sections 12.4 to 12.7 for the study's statistical plan.

This approach will be considered feasible if 17 or more patients are able to complete neoadjuvant treatment and proceed with surgical resection of disease. If 4 or more patients are unable to complete neoadjuvant treatment due to toxicity or tumor progression, or have unresectable disease at the time of surgery, this approach will be considered unfeasible. Patients who decline immunotherapy or surgery due to reasons not related to toxicity or tumor progression, will not be considered a treatment failure.

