## **12.3 Interim analyses**

Accrual will be limited to no more than 6 patients at a given window of immunotherapy dosing and 10 days post recovery from surgery. Toxicity and treatment failures will be reviewed prior to each additional patient accrual. If the number of patients who fail neoadjuvant treatment exceeds the maximum number allowable to achieve the primary objective, the study will be stopped early (i.e. treatment failure in 4 patients).

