### 12.7.2 Sample size justification

The primary objective is to determine the feasibility of three doses of atezolizumab prior to surgery in patients with advanced cutaneous squamous cell carcinoma. The sample size of evaluable 20 patients allows at least 80% power to reject the null hypothesis of 50% if the true fraction is above 80% (or a difference  $>30\%$ ) using binomial enumeration of all possible outcomes, with a test at the 5% significance level. We expect the true fraction is 85%, which means that we are well powered to detect an effect size that is bigger than 30%.

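### The early-stopping rule (7.2, 12.3) and the feasibility decision (12.1) do not count the same failures, so the stated stopping rules conflict

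*Combined protocol and SAP*

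**What the plan says.** Four places define failure or act on a count of failures.

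- **Section 7.2** gives the stop in two sentences. One gives the purpose and the causes: early stopping applies once the count of those that "fail to complete the neoadjuvant protocol (due to drug related toxicity or tumor progression) is such that the primary objective would be unachievable". Another sets the number at four patients who do not complete the neoadjuvant protocol, and names no cause.
- **Section 12.1** requires 17 or more successes for feasibility. Four or more failures make the approach unfeasible, through toxicity or tumor progression that prevents completion, "or have unresectable disease at the time of surgery, this approach will be considered unfeasible". Patients who decline immunotherapy or surgery for unrelated reasons are not treatment failures.
- **Section 12.3** restates the stop, with review before each new accrual: "the study will be stopped early (i.e. treatment failure in 4 patients"). It ties the count to the maximum compatible with the primary objective but lists no causes.
- **Sections 1.1 and 10.1** define the patient-level outcome: "The treatment will be evaluated as non-feasible for patients who have disease progression during neoadjuvant treatment", for those who discontinue because of toxicity, and for those who cannot have curative resection after three cycles.

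**The concern.** The stop in 7.2 is meant to end the study once the primary objective is out of reach. It can do so only if it counts the same events as the decision in 12.1. The event missing from the 7.2 parenthesis, loss of resectability, is the risk that section 2.3 names for this design and that section 10.1 gives as a reason for choosing feasibility as the endpoint. If the site counts by the parenthesis, further patients with resectable tumors could have surgery postponed in a study that can no longer succeed. If it counts by 12.3 read with 12.1, the study stops. A site following the document cannot tell which rule binds.

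A second inconsistency affects the endpoint. Progression during neoadjuvant treatment is non-feasible in 1.1 and 10.1 without qualification. In 12.1, progression counts only if it prevents completion or leaves the disease unresectable.

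**Working it through.** **Inputs from the documents.** Section 3: screening is "will be screened for enrollment in this study to yield 20 evaluable patients". Section 12.7.2: the sample size "allows at least 80% power to reject the null hypothesis of 50% if the true fraction is above 80"%, "using binomial enumeration of all possible outcomes, with a test at the 5% significance level", and "We expect the true fraction is 85"%. Section 12.1: 17 or more successes is feasible, 4 or more failures is unfeasible. Section 12.5: 3 failures expected, so 3/20 = 15% total failure.

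**Input not in the documents.** The proportion u of patients who complete three doses and are then unresectable. I take u from 0% to 5%.

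**Step 1: the plan's own power figure.** With X ~ Bin(20, p), the smallest cut-off r with P(X ≥ r | 0.50) ≤ 0.05 is 15: P = 0.0207, against 0.0577 at r = 14. Power at 0.80 is P(X ≥ 15 | 0.80) = 0.804, so the stated 80% reproduces. It belongs to a cut-off of 15 of 20. At 17 of 20 the figures are 0.0013 under 50%, 0.411 under 80% and 0.648 under 85%. That discrepancy is a separate matter, but it means that four failures put the objective out of reach only under the 17 of 20 rule.

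**Step 2: is the number four consistent?** Treating every patient as a success or a failure, 20 − 4 = 16 < 17. The number agrees across 7.2, 12.1 and 12.3. What differs is which failures are counted.

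**Step 3: one case under each rule.** Three patients stop for drug-related toxicity or progression. A fourth completes three doses and is unresectable.

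| Text | Count | Result |
|---|---|---|
| 12.1 | 4 | unfeasible |
| 7.2 parenthesis | 3 | accrual continues |
| 7.2 last sentence | 3, or 4 if the protocol is taken to include surgery | unclear |
| 12.3 read with 12.1 | 4 | study stops |

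The last sentence of 7.2 also departs from 12.1 in the other direction. With no cause named, it could count a patient who declines further immunotherapy for unrelated reasons.

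**Step 4: size.** Hold total failure at 15%. Failures counted by the 7.2 parenthesis then occur at rate 0.15 − u. The chance that a trial is unfeasible under 12.1 while the 7.2 count stays below four is

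P(Bin(20, 0.15) ≥ 4) − P(Bin(20, 0.15 − u) ≥ 4).

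| u | P(12.1 count ≥ 4) | P(7.2 count ≥ 4) | Difference |
|---|---|---|---|
| 0% | 0.352 | 0.352 | 0 |
| 1% | 0.352 | 0.304 | 0.048 |
| 2% | 0.352 | 0.257 | 0.095 |
| 3% | 0.352 | 0.213 | 0.140 |
| 5% | 0.352 | 0.133 | 0.219 |

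**Step 5: extra patients.** Take u = 5% and suppose each outcome is known before the next accrual. The 7.2 count then enrolls about 3.4 patients beyond the fourth failure per trial that ends unfeasible, or 0.352 × 3.4 ≈ 1.2 averaged over all trials. But 7.2 and 12.3 allow six patients in the window at once. If five others are already enrolled at the fourth failure under either rule, the 3.4 falls to about 1.1.

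**Step 6: the progression wording.** Take a patient who receives all three doses, progresses before surgery and is resected. Under 1.1 and 10.1 this is non-feasible, if the days after dose 3 belong to the neoadjuvant treatment period; the 21-day cycle makes that a natural reading. Under 12.1 the patient completed treatment and was not unresectable, so is a success.

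**The case against.** The strongest reply is that the document as a whole already stops the trial. Section 12.3 is the interim-analysis section. It carries no cause restriction, it is tied to the primary objective, and it is applied before each accrual. Section 12.1 uses the term treatment failure for surgery as well as immunotherapy. On that reading unresectable patients count, and the last sentence of 7.2 does not contradict it. This stands as a reading, and it defeats the inference a reader might draw that the trial would necessarily keep enrolling after feasibility is lost. It does not remove the conflict. Section 12.3 lists no causes and speaks of patients who fail neoadjuvant treatment, while 12.1 and the study calendar in section 9 treat surgery as a separate step.

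Second, patients not eligible for standard resection are excluded at entry, so later unresectability will often be progression, a cause that 7.2 names. That narrows the gap. Yet a patient who received all three doses has not failed to complete them.

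Third, the unresectable rate may be very low. In the precedents in section 2.3, all 20 patients proceeded to surgery in the skin cancer pilot, and 20 of 21 had complete resection in the lung study. This is fair, and it is why the range above includes 0%. The precedents do not establish zero: 1 of 21 is 4.8%, and 0 of 20 has a one-sided 95% upper limit of 1 − 0.05^(1/20) = 13.9%.

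On the progression wording, formal RECIST measurement is required only at baseline and after cycle 2, so progression after dose 3 will seldom be formally documented. The inconsistency is real but narrow.

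**Conclusion.** The stop and the decision use the same number, four, but different lists of failures, and the stopping texts in 7.2 and 12.3 can give opposite instructions for the same patients. The consequence ranges from nothing, if no patient is unresectable after three doses, to about 22% of trials ending unfeasible without the 7.2 count reaching four, if 5% are. That rests on 15% total failure, independent patients and a literal use of the 7.2 parenthesis. The number of extra patients exposed is smaller than a one-at-a-time calculation suggests.

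Two larger figures are tempting and not supported. Adding 10% unresectable to 15% other failures gives 0.775 − 0.352, about 42% of trials, but it assumes 25% total failure against the 15% the protocol expects. At a true 85% success rate, 24% of trials end on exactly 17. That is not the chance that the verdict flips, which also requires a patient who progressed after dose 3 and was still resected; no rate for that is given.

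This is a should-fix: the correction is specific and cheap, and it bears on when the study stops postponing surgery.

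**What to change.** - In 7.2 and 12.3, count toward the four every patient who is a failure under 12.1, including those with unresectable disease at surgery. Exclude the unrelated refusals that 12.1 excludes. Simplest is to define treatment failure once in 12.1 and refer to it from both sections, replacing the 7.2 parenthesis.
- Reconcile 1.1 and 10.1 with 12.1 on progression in a patient who is still resected. Either definition can be applied consistently. Limiting progression failures to those that prevent completion or resection would relax the endpoint as 1.1 and 10.1 now state it, so the choice is the sponsor's. One definition should then be used throughout.

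The cost is an amendment to wording, with no added patients or procedures. With the 17 of 20 decision and the 12.1 failure list unchanged, aligning the stop leaves the probability of declaring feasibility unchanged. The downside is that the study may stop slightly earlier than under the 7.2 wording.

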### 7.2.1 Adverse Events

An AE is any unfavorable and unintended sign, symptom, or disease temporally associated with the use of an investigational medicinal product (IMP) or other protocol-imposed intervention, regardless of attribution.

This includes the following:

- AEs not previously observed in the subject that emerge during the protocol-specified AE reporting period, including signs or symptoms associated with cutaneous squamous cell carcinoma that were not present prior to the AE reporting period.
- Complications that occur as a result of protocol-mandated interventions (e.g.,

invasive procedures such as cardiac catheterizations).

- If applicable, AEs that occur prior to assignment of study treatment associated with medication washout, no treatment run-in, or other protocol-mandated intervention.
- Preexisting medical conditions (other than the condition being studied) judged by the investigator to have worsened in severity or frequency or changed in character during the protocol-specified AE reporting period.

### **7.2.2 Serious Adverse Events**

An AE should be classified as an SAE if any of the following criteria are met:

- It results in death (i.e., the AE actually causes or leads to death).
- It is life threatening (i.e., the AE, in the view of the investigator, places the subject at immediate risk of death. It does not include an AE that, had it occurred in a more severe form, might have caused death.).
- It requires or prolongs inpatient hospitalization.
- It results in persistent or significant disability/incapacity (i.e., the AE results in substantial disruption of the subject's ability to conduct normal life functions).
- It results in a congenital anomaly/birth defect in a neonate/infant born to a mother exposed to the IMP.
- It is considered a significant medical event by the investigator based on medical judgment (e.g., may jeopardize the subject or may require medical/surgical intervention to prevent one of the outcomes listed above).

### **7.2.3 Adverse Events of Special Interest**

AESIs are a subset of Events to Monitor (EtMs) of scientific and medical concern specific to the product, for which ongoing monitoring and rapid communication by the Investigator to the Sponsor is required. Such an event might require further investigation in order to characterize and understand it. Depending on the nature of the event, rapid communication by the trial Sponsor to other parties (e.g., Regulatory Authorities) may also be warranted.

The following AEs are considered of special interest and must be reported to the Genentech Drug Safety expeditiously, irrespective of regulatory seriousness criteria:

- Cases of potential drug-induced liver injury that include an elevated ALT or AST in combination with either an elevated bilirubin or clinical jaundice, as defined by Hy's Law and based on the following observations:
  - Treatment-emergent ALT or AST  $> 3 \times$  ULN in combination with total bilirubin  $> 2 \times$  ULN
  - Treatment-emergent ALT or AST  $> 3 \times$  ULN in combination with clinical jaundice
- Suspected transmission of an infectious agent by the study treatment (STIAMP), as defined below:
  - Any organism, virus, or infectious particle (e.g., prion protein transmitting transmissible spongiform encephalopathy), pathogenic or non-pathogenic, is considered an infectious agent. A transmission of an infectious agent may be suspected from clinical symptoms or laboratory findings that

indicate an infection in a patient exposed to a medicinal product. This term applies only when a contamination of study treatment is suspected.

The Atezolizumab Events of Special Interest Are:

- Systemic lupus erythematosus
- Events suggestive of hypersensitivity, infusion-related reactions, cytokine-release syndrome, macrophage activating syndrome, hemophagocytic lymphohistiocytosis
- Nephritis
- Ocular toxicities (e.g., uveitis, retinitis, optic neuritis)
- Grade  $\geq 2$  cardiac disorders (e.g., atrial fibrillation, myocarditis, pericarditis)
- Vasculitis
- Autoimmune hemolytic anemia
- Severe cutaneous reactions (e.g., Stevens-Johnson syndrome, dermatitis bullous, toxic epidermal necrolysis)
- Facial Paresis
- Myelitis

### **7.3 Methods and Timing for Assessing and Recording Safety Variables**

The investigator is responsible for ensuring that all AEs and SAEs that are observed or reported during the study, are collected and reported to the FDA, appropriate IRB(s), and Genentech, Inc. in accordance with CFR 312.32 (IND Safety Reports).

#### **7.3.1 Adverse Event Reporting Period**

The study period during which all AEs and SAEs must be reported begins after informed consent is obtained and initiation of study treatment and ends 30 days following the last administration of study treatment or study discontinuation/termination, whichever is earlier. After this period, investigators should only report SAEs that are attributed to prior study treatment.

All adverse events (AEs), regardless of seriousness or relationship to study drug, are to be collected only on designated study dates from signing of informed consent through 30 days after administration of study drug, and recorded in the study-specific worksheets, with the following exceptions:

- AEs that are solely laboratory values; are not related to the study drug; AND are clinically non-significant may not be collected.
- Non serious AEs that are not related to the study drug; are not clinically significant; AND are expected in the post-surgery clinical setting may not be collected.
- SAEs that occur from signing of informed consent to prior to administration of study agent may not be collected unless assessed as possibly, probably or definitely-related to a study procedure.

All patients enrolled in this study receive surgical intervention in the course of their standard of care. As a consequence of this surgery, patients may experience certain

expected and normal adverse events. The following post-operative adverse events will be captured only in the patient's Electronic Health Record (EHR) source documentation and not in the adverse event log. If the adverse event exceeds the grading listed below or occurs outside the post-operative time window, the adverse event will be recorded in the Adverse Event Logs.

- Surgical wound site and associated, expected secondary signs and symptoms, including:
  - CTCAE v5.0 Grade 1 pain associated with surgical wound, including headaches – mild pain, little to no limit on adult daily life.
  - CTCAE v5.0 Grade 1 weight loss, anemia, and electrolyte abnormalities.

